Full study protocol and statistical analysis plan

Official Title of the study:

Serum Thiol/Disulphide Homeostasis level and its correlation with the severity of preeclampsia

Date of the document:

April 2019.

Contents:

- 1. Participant Flow
- 2. Baseline Characteristics
- 3. Outcome Measures
- 4.Endpoints of the study
- 5. Limitations and Strengths
- 6. Certain Agreements
- 7. Results Point of Contact

1. Participant Flow

Recruitment Details

This was an observational prospective cohort study conducted at Obstetrics and Gynecology Department of Cengiz Gokcek Obstetrics and Children's Hospital between April and October 2019. One hundred women will enrolled in the study in two groups. We will consecutively recruit 50 pregnancies complicated with preeclampsia, and 50 healthy pregnancies will select for the control group. All patients will gave their oral and written informed consent before their inclusion in the study.

Pre-assignment Details

We firstly will assess the recruited people to ensure meeting the inclusion and exclusion

criteria.

The inclusion criteria are made according to the official documents.

Arm/Group Information *

There are two groups in the study.

Arm/Group Title *

Preeclampsia group = Group A Control group= Group B

2. Baseline Characteristics

Frequency and percentage analysis will be used for some variables during data analysis. In addition, independent samples t-test (Student's t-test) will be used for comparison of the thiol/disulfide levels by the variable groups formed. The SPSS (IBM SPSS Statistics for Windows, Version 22.0. IBM Corp. NY, USA) statistical program will be used for all statistical calculations.

3. Outcome Measures

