Every women in the study population will undergo obstetric ultrasound examination and fetalmaternal assessment will carry out by one of the authors. The obstetric anamnesis will obtain from all subjects. The dempograhic data like age, gravidity, parity, BMI and gestational age will record. Maternal venous blood samples will take for measurement of thiol and disulphide levels after the diagnosis of preeclampsia in outpatient clinic. These samples quickly will centrifuge at 1,500 g for 10 min, serum samples will separate and store at -80 C until the day of measurement. All patients with early onset preeclampsia will hospitalize. A betamethasone injection will administer immediately after hospitalization. The pregnancy will immediately terminate in emergencies arising from maternal or fetal causes. Otherwise, blood pressure will measured every four hours during periods of rest. Hypertension can will be confirmed within a shorter interval in patients with blood pressure ≥ 110 mm Hg diastolic and ≥ 160 mm Hg systolic in order to give timely antihypertensive treatment. Delivery will postpone for at least 24-48 hours if maternal/fetal status permit. A betamethasone injection for lung maturation (two dosages of 12 mg at 24 h intervals) will give within the said period. The control group's samples will obtaine during routine obstetrical care examination in the third trimester of pregnancy. Then these pregnant women will follow-up until delivery. All patients with late onset preeclampsia (LOPE) will also hospitalize and terminate. The control groups' samples will obtaine during the routine obstetrical care examination in the third trimester of pregnancy. Then these pregnant women were follow-up until the delivery. Both groups will compare in terms of maternal age, BMI, gravida, parity, week of gestation, systolic/diastolic blood pressure, total protein in spot urine sample, white blood cell (WBC) count, hemoglobin, platelet count, blood urea nitrogen, creatinine, liver function tests (AST, ALT), thiol, disulphide, and infant weight at delivery. Blood samples were separated by centrifugation for 10 minutes at 1500 g after clotting for 30 minutes at room temperature. The serum samples were subsequently stored in aliquots at -80°C prior to the analysis of thiol/disulphide levels. The contents of the native thiol (-SH) and total thiol (-SH + -S-S-) in the serum samples will measure using the reagent kits from Rel Assay Diagnostics (Gaziantep, Turkey). These spectrophotometric methods, developed by Erel and Neselioglu,(1) will assay in an auto-analyzer. The reducible disulfide bonds will first reduce to free-form functional thiol groups. The unused reductant, sodium borohydride, will consume and remove with formaldehyde, and all of the thiol groups, including the reduced and native ones, will measure after reacting with 5,5'-dithiobis-(2-nitrobenzoic) acid (DTNB). Half of the difference between the total and native thiols will yield the dynamic disulfide (-S-S) content.

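### Maternal age, BMI, parity and gestational week are recorded but not used in the preeclampsia-versus-control marker comparison, so any imbalance related to the markers carries into the estimated difference

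*Combined protocol and SAP*

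**What the plan says.** Section 1 (Recruitment Details) describes the design as observational and sets the group sizes: "We will consecutively recruit 50 pregnancies complicated with preeclampsia, and 50 healthy pregnancies will select for the control group". Cases are consecutive. The rule for selecting controls is not given, and no matching, stratification or restriction on maternal characteristics is stated.

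Section 3 lists the maternal data: "The dempograhic data like age, gravidity, parity, BMI and gestational age will record". Their stated use is that "Both groups will compare in terms of maternal age, BMI, gravida, parity, week of gestation" and on a run of clinical and laboratory variables. Thiol and disulphide appear in that same list.

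Section 2 names one inferential method: "independent samples t-test (Student's t-test) will be used for comparison of the thiol/disulfide levels by the variable groups formed". The only other analysis there is descriptive: "Frequency and percentage analysis will be used for some variables during data analysis". The document contains no regression, analysis of covariance or other adjusted estimate. Section 5 gives one limitation, other oxidative parameters that were not measured, and does not mention confounding.

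**The concern.** When groups are defined by having or not having a disease, nothing in the design balances age, body size, parity or gestational week between them. If one of these differs between the groups and is also related to the marker, an unadjusted t-test counts its contribution as part of the group difference. Comparing the groups on that covariate may reveal the imbalance but does not remove it, and the plan does not say what follows if one is found.

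The first half of the primary endpoint in section 4, thiol/disulphide levels in preeclampsia, is at stake. Depending on sign, the carried-over difference could add to a true difference, hide one, or produce one where the disease itself makes none.

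Gestational week deserves particular attention because the document itself points to a possible imbalance. Section 3 has controls sampled in the third trimester and cases sampled after diagnosis, early-onset cases included.

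**Working it through.** **Inputs from the document.** 50 preeclampsia and 50 control pregnancies (section 1); an unadjusted two-sample t-test (section 2). The document gives no power calculation, alpha, effect size or SD, so there is no planned figure to reproduce.

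**Assumptions.** Two-sided alpha 0.05, no dropout, marker SD 1. One covariate differs by d SD between groups, has within-group correlation r with the marker, and there is no group difference once it is held fixed. I used d = 0.3 to 0.8 and r = 0.1 to 0.4; neither range comes from the document.

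**Step 1: bias and rejection rate of the t-test.** The bias in the raw mean difference is d × r marker SDs. The standard error is √(2/50) = 0.2, so the noncentrality is d × r / 0.2 = 5 × d × r, on 98 degrees of freedom. For d = 0.5, r = 0.3 the bias is 0.15 SD, the noncentrality is 0.75 and the test rejects 11.5% of the time. Each cell gives bias in SD, then rejection rate:

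| d | r = 0.1 | r = 0.2 | r = 0.3 | r = 0.4 |
|---|---|---|---|---|
| 0.3 | 0.03; 5.3% | 0.06; 6.0% | 0.09; 7.3% | 0.12; 9.1% |
| 0.5 | 0.05; 5.7% | 0.10; 7.9% | 0.15; 11.5% | 0.20; 16.8% |
| 0.8 | 0.08; 6.8% | 0.16; 12.4% | 0.24; 22.1% | 0.32; 35.4% |

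With d = 0 or r = 0 the rate is 5%.

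**Step 2: the same data with the covariate in the model.** In simulations of 4,000 runs each, rejection under no true effect was:

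- d = 0.5, r = 0.2: t-test 8.2%, adjusted 5.1%
- d = 0.5, r = 0.3: t-test 10.6%, adjusted 5.1%
- d = 0.8, r = 0.3: t-test 21.4%, adjusted 4.8%

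**Step 3: what the covariate comparison can detect.** If the covariates were tested at 5%, the smallest significant difference at 50 v 50 would be 1.984 × 0.2 = 0.397 SD. Just below it, at d = 0.39, the marker test rejects 5.4%, 6.7%, 8.9% and 12% of the time for r = 0.1, 0.2, 0.3 and 0.4. A true imbalance of d = 0.8 (noncentrality 4) would be significant about 98% of the time.

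**Step 4: masking.** Take a true difference of 0.6 SD and an opposing imbalance (d = −0.5, r = 0.3). The noncentrality falls from 5 × 0.6 = 3.0 to 5 × (0.6 − 0.15) = 2.25, and t-test power falls from 84% to about 60%. The adjusted model keeps about 84%.

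**Step 5: the price of adjusting.** With covariates independent within groups, adjustment multiplies the standard error by about √[(1 + Σd²/4)(1 − Σr²)].

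- One covariate, d = 0.8, r = 0.1: √(1.16 × 0.99) = 1.072; noncentrality 3.0/1.072 = 2.80; power about 79%.
- Three covariates, each d = 0.5, r = 0.1: √(1.1875 × 0.97) = 1.073; power again about 79%.
- Four covariates, each d = 0.5, r = 0.1: √(1.25 × 0.96) = 1.095; noncentrality 2.74; power about 77%.
- One balanced covariate, r = 0.3: √0.91 = 0.954; noncentrality 3.14; power about 88%, a small gain on 84%.

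**The case against.** The strongest reply is that the study is descriptive. The title speaks of correlation and section 4 of evaluating levels in preeclampsia; neither states a causal or covariate-conditional effect. For a plain contrast of affected and healthy pregnancies, the unadjusted difference is a legitimate quantity, and the rejections in Step 1 would be real marginal differences. This stands as a reason to keep the t-test. It does not remove the need for an adjusted estimate, because readers will attribute a difference between these groups to the disease.

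Second, confounding needs the covariates to be related to both group and marker, and the document is silent on the second link. That stands: with r near zero the inflation is trivial.

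Third, a reader might infer that imbalances too small to be significant would drive the error rate to 22–35%. The figures do not support that. Those rates need d = 0.8, which a 5% covariate test would almost always flag; below the 0.397 SD threshold the rate is about 5–12% over the r values used. Nor does the document say how the covariate comparison will be tested or read, so it cannot be claimed that a non-significant result would be taken as proof of similar groups.

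Fourth, restriction or matching may exist in the eligibility documents that section 1 refers to without setting out. It cannot be excluded, but it is not stated here. If it exists, the plan should say so and the analysis should reflect it.

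**Conclusion.** The point holds as a gap in the analysis plan. Non-randomised groups with no stated matching are compared on the markers by an unadjusted t-test, although the main maternal covariates are recorded. Any imbalance in a covariate related to the markers would carry into the estimate.

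The size cannot be fixed from the document. Under the assumed values it runs from negligible (5–7% rejection at r = 0.1) through 7–22% at r = 0.3 to 35% at d = 0.8, r = 0.4. These figures rest on one covariate, a linear relation and two-sided alpha 0.05.

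Three stronger readings are not supported: that the planned comparison will be materially biased, that adjusting for the recorded variables would eliminate confounding, and that adjustment is free. The near-5% rate in Step 2 belongs to a correctly specified model. The point concerns the preeclampsia-versus-control comparison only, not the severity half of the endpoint.

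**What to change.** In section 2, pre-specify for each thiol/disulphide marker a linear regression on group, maternal age, BMI, nulliparity (yes/no) and gestational week at blood sampling. Report the adjusted mean difference with its 95% CI alongside the unadjusted t-test. Gravidity overlaps with parity and can be left out. Also:

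- State when BMI is measured, preferring a pre-pregnancy or early-pregnancy value if one is recorded. A value taken after diagnosis may partly reflect the disease.
- State that gestational week means the week of the blood draw. If any case is sampled before the third trimester, no control covers that week and the model extrapolates; report the overlap.
- Do not choose covariates by baseline p-values.
- Do not adjust for consequences of the disease: blood pressure, urine protein, liver tests, infant weight.
- Describe how controls are selected, including any matching or restriction.
- Add residual confounding to the limitations in section 5.

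The cost is a few sentences and one further SPSS procedure, with no extra patients. The listed variables are already collected, subject to confirming the timing of BMI and gestational week. One hundred women can support a model with group and four covariates. The statistical price is the modest power loss in Step 5 when covariates are imbalanced but weakly related to the marker.

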
4. Endpoints of the study:

The primary endpoint in this analysis is to evaluate thiol/disulfide levels in preeclampsia and address its relationship with its severity.

5. Limitations and strengths:

This study has a limitation that other oxidative parameters such as lipid hydroperoxide, total antioxidant status, total oxidant status and oxidative stress index were not measured.

6. Certain Agreements

The authors declare that they have no conflict of interest.

7. Results Point of Contact

Corresponding Author: [name], Cengiz Gokcek Public Hospital, Department of Obstetrics and Gynecology, Gaziantep/Turkey, [contact]

Adress: [name]

GSM: [contact]

Reference

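### Does comparing raw infant weight between the groups, without standardising for gestational age at delivery, undermine the analysis?

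*Combined protocol and SAP*

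**What the plan says.** Section 3 (Outcome Measures) gives one long list of variables on which the two groups will be compared: maternal characteristics, week of gestation, blood pressure, urine protein, blood count, renal and liver tests, and finally "thiol, disulphide, and infant weight at delivery". No covariate, centile, z-score or matching is attached to infant weight.

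Gestational age appears twice in that section. It is among the recorded baseline items ("The dempograhic data like age, gravidity, parity, BMI and gestational age will record"), and it appears as week of gestation in the comparison list. Neither mention says whether it refers to blood sampling or to delivery.

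The same section describes how pregnancies end. In Group A: "The pregnancy will immediately terminate in emergencies arising from maternal or fetal causes"; for early-onset cases otherwise, "Delivery will postpone for at least 24-48 hours if maternal/fetal status permit"; and "All patients with late onset preeclampsia (LOPE) will also hospitalize and terminate". For controls: "Then these pregnant women will follow-up until delivery".

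Section 2 (Baseline Characteristics) names Student's t-test only for "comparison of the thiol/disulfide levels by the variable groups formed". Section 4 (Endpoints of the study) states: "The primary endpoint in this analysis is to evaluate thiol/disulfide levels in preeclampsia", together with the relation to severity. Infant weight is not mentioned there.

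**The concern.** Birth weight rises with gestation. In Group A the disease itself can prompt delivery, whereas controls are healthy pregnancies followed until they deliver, and no matching on gestation is described. Mean gestation at delivery is therefore likely to be shorter in Group A, and a raw weight difference would include that gap.

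A reader of the group table could take a lower mean weight as evidence of impaired fetal growth when some or all of it is earlier birth. If week of gestation means gestation at sampling, the table would not show the gap in gestation at delivery either. What is at stake is the reading of one secondary line in a descriptive table.

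**Working it through.** **There is no figure in the plan to reproduce.** The documents give no birth weight, SD, gestation at delivery, split between early and late onset, significance level or power. The only usable input is 50 women per group (Section 1, Participant Flow).

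**Step 1. What the listed variables allow.**
- If week of gestation means at delivery, the table already shows the gestation gap beside the weight gap.
- If it means at sampling, the table does not show it. Gestation at delivery is then gestation at sampling plus the days from sampling to delivery divided by 7. Gestational age is recorded and weight at delivery is collected in both groups, so this can be derived if sampling and delivery dates are kept.

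The text does not settle which reading is meant. On neither reading is separation ruled out.

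**Step 2. How large the gestation component could be.** Assumptions, none of them in the documents: weight gain of 100 to 200 g per week, weight SD of 500 to 800 g, a two-sided 5% t-test, and no weight deficit at equal gestation.

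Standard error of the difference = SD × √(2/50) = SD × 0.2, which is 100 g at SD 500 and 160 g at SD 800.

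95% CI half-width = 1.984 × SE (t with 98 degrees of freedom), which is 198 g and 318 g. Divided by 200 and then 100 g per week, these equal about 1.0 to 2.0 weeks of gestation (SD 500) and 1.6 to 3.2 weeks (SD 800).

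Difference due to gestation = weekly gain × gap in weeks. Probability of p<0.05 from the noncentral t with noncentrality difference/SE:

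| Difference | Gaps that give it | SD 500 | SD 800 |
|---|---|---|---|
| 100 g | 1 week at 100 g | 0.17 | 0.095 |
| 200 g | 1 week at 200 g, or 2 at 100 g | 0.51 | 0.24 |
| 400 g | 2 weeks at 200 g, or 4 at 100 g | 0.98 | 0.70 |
| 800 g | 4 weeks at 200 g | 1.00 | 1.00 |

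**Step 3. Gestation's share of the raw difference.** Share = gestation part / (gestation part + deficit at equal gestation), with the deficit assumed to lie between 0 and 600 g.
- 100/(100 + 600) = 14%
- 200/(200 + 400) = 33%
- 800/(800 + 200) = 80%
- any gap with zero deficit = 100%

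**Step 4. What these figures mean.** They cover nearly the whole possible range, and every input except the group size is assumed. A significant result arising from gestation alone would also not be a false positive for the comparison as listed: the infants in Group A really would be lighter on average. It would mislead only if read as a growth effect at equal gestation, which the plan nowhere proposes.

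**Step 5. Effect on the study's question.** Infant weight does not enter the thiol/disulphide comparison or the severity question as the plan describes them. Changing how weight is summarised leaves both as they are.

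**The case for a change.** The strongest case for a change is that the remedy is cheap and helps on either reading of week of gestation. Two separate group means, one for gestation and one for weight, do not show whether the infants were small for their gestation. A gestation-specific z-score or centile would, and it needs only one date-derived variable and one named reference. The way deliveries are described makes a gestation gap likely, so the raw line will probably need a caveat.

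Some of this stands. The gestational-week item has no time point, no weight-for-gestation measure is specified, and a raw difference alone cannot be apportioned. It does not show an error in the plan. Standardising answers a different question from the one listed, because it removes the part of the weight difference that runs through earlier delivery, which preeclampsia partly causes. The raw means would therefore have to stay, and the z-score would be an additional statistic on a variable that is not an endpoint. It would also need an external birth-weight reference and, for a sex-specific version, infant sex, which is not among the listed variables.

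**Conclusion.** No change to the plan is needed. Followed as written, it yields a valid unadjusted total difference in infant weight, presented as one item in a descriptive comparison, with no growth claim resting on it. The undated gestational week is a gap in wording that an analyst would ordinarily fill when labelling the table, by stating whether the figure refers to sampling or delivery and presenting the weight comparison as unadjusted.

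The contribution of gestation cannot be sized from the documents. The illustrative ranges (about 0.1 to 1.00 for a significant difference from gestation alone, and 14% to 100% for its share) depend entirely on the assumed weekly gain, SD, gap and deficit. The effect on the primary thiol/disulphide result is nil. The conclusion rests on infant weight staying descriptive: a report that drew a conclusion about fetal growth from the raw means would need a gestation-standardised measure to support it.

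### The title and the only primary endpoint ask about severity, but severity is not defined and no analysis within the preeclampsia group is specified

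*Combined protocol and SAP*

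**What the plan says.** All references are to the combined protocol and SAP.

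- **Title:** "Serum Thiol/Disulphide Homeostasis level and its correlation with the severity of preeclampsia".
- **Section 4, the only endpoint:** "The primary endpoint in this analysis is to evaluate thiol/disulfide levels in preeclampsia and address its relationship with its severity".
- **Section 1, Arm/Group Information:** "There are two groups in the study". They are Group A (preeclampsia, 50 women) and Group B (healthy controls, 50 women).
- **Section 2, statistical methods:** frequencies and percentages for some variables, and then "independent samples t-test (Student's t-test) will be used for comparison of the thiol/disulfide levels by the variable groups formed". No other inferential method appears anywhere.
- **Section 3, clinical and laboratory variables:** "Both groups will compare in terms of maternal age, BMI, gravida, parity, week of gestation, systolic/diastolic blood pressure, total protein in spot urine sample". The list goes on to "platelet count, blood urea nitrogen, creatinine, liver function tests (AST, ALT), thiol, disulphide, and infant weight at delivery". It is a list for comparing the two groups.
- **Section 3, early and late onset:** these terms appear in the text on care, for example "All patients with early onset preeclampsia will hospitalize". No gestational week separates them.
- **Section 3, 160 systolic and 110 diastolic:** this level appears only where hypertension may be confirmed at a shorter interval.
- **Section 1, Pre-assignment Details:** "The inclusion criteria are made according to the official documents".

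The word severity occurs only in the title and in section 4.

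**The concern.** A primary endpoint needs a variable, a population and a method. For the severity half of this endpoint the plan gives none of the three. The title speaks of correlation, yet no correlation or regression is planned.

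Two things can follow. If the plan is carried out as a comparison of A with B, the study ends without a severity result. If subgroups are formed later, the marker, measure, time point and cut can all be settled with the data in view, and a nominal 5% test no longer has a 5% error rate. Either way, a statement about severity in the report could not be traced to a pre-specified analysis.

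**Working it through.** **Step 1. Can the stated test answer the stated question?** A t-test of A against B takes two inputs per woman: her thiol or disulphide level and her group label. The label is the same for all 50 women in Group A, so differences in severity among them do not enter the test. It can answer whether levels differ in preeclampsia. It cannot answer whether they vary with severity within preeclampsia.

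**Step 2. Does any other text supply the missing definition?**

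| Candidate | Where | Role in the plan | Called severity? |
|---|---|---|---|
| Early or late onset | Section 3 | Care pathway, no week given | No |
| 160 systolic and 110 diastolic | Section 3 | Interval for confirming hypertension | No |
| Systolic and diastolic pressure, spot-urine protein, platelets, creatinine, AST, ALT | Section 3 | Comparison of the two groups | No |
| Official documents | Section 1 | Inclusion criteria | No |

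The thiol side is open as well. Section 3 measures native and total thiol and derives disulphide as half their difference, and no one of these is named for the severity question.

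**Step 3. What could a free choice do?** This is an illustration only. The documents give no alpha, so two-sided 0.05 is assumed, with n = 50 cases and no true relation. The cuts and measures below were chosen for this review.

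- *Three cuts of one measure* (25/25, 15/35, 10/40), Student t-test for each. If the tests were independent, the chance of at least one p<0.05 would be 1 − 0.95³ = 0.143. They share the same women, so the true figure is lower. Simulation with 200,000 samples gives 0.114, and a repeat with 100,000 gives 0.115.
- *Seven graded measures against one marker* (the seven in the third row of the table), Pearson test for each. If the measures were independent, the chance would be 1 − 0.95⁷ = 0.302. Independence is implausible for pairs such as systolic with diastolic pressure or AST with ALT. With a common correlation of 0.3 between measures, simulation (100,000 samples) gives 0.272. With 0.6 it gives 0.207.

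**Step 4. What can 50 cases show?** By Fisher's z, the correlation detectable with 80% power is r = tanh[(1.960 + 0.842)/√(50 − 3)] = tanh(2.802/6.856) = tanh(0.409) = 0.39. This limits any severity analysis here and is not itself the defect. The plan gives no sample-size calculation to reproduce; the only check available is 50 + 50 = 100, which agrees.

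**The case against.** The strongest reply is that section 2 does not tie the t-test to Groups A and B. It speaks of groups that are formed, and section 3 names early and late onset, so a subgroup test within preeclampsia may have been intended. This is a fair reading, and it means the plan cannot be said to exclude a severity analysis. It does not close the gap. Section 1 states two groups, onset is never linked to severity, and no cut is given.

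A second reply is that the error rates in the working rest on cuts and measures the plan never says will be tried. That stands: they show what the open choice permits, not what the investigators will do.

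A reader might also infer more than the documents support:

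- **That controls will be pooled into a correlation.** No text proposes it.
- **That a graded measure is always better than a severe/non-severe split.** Which has more power depends on the unknown shape of the relation. The defect is the absence of any definition.
- **That the four-hourly pressure readings are rival severity values at the blood draw.** Those readings follow hospitalisation, whereas the sample is taken after diagnosis in the outpatient clinic. What remains true is that no reading is designated.

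The gap does not look like an effect of redaction or text extraction, because the sections on groups, statistics and endpoints read as complete.

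**Conclusion.** The point holds. As written, the analysis cannot deliver the severity half of the sole primary endpoint, nor the correlation in the title. This conclusion comes from the text and depends on no assumed figure. It should be corrected before any severity result is reported as pre-specified.

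The size of the harm is conditional. Under the A-versus-B reading, the severity question has no result. Under the subgroup reading, the false-positive rate could rise from 5% to about 11% with three cuts, or to about 21% to 27% with seven correlated measures, on the assumptions stated in the working. It would be too strong to say that the plan forbids a severity analysis or that its error rate is inflated by those amounts. The plan is silent, and the figures only show the room that silence leaves.

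**What to change.** 1. Keep the t-test for A versus B.
2. Add one primary severity analysis in the 50 Group A women only: one named thiol marker against one named severity measure recorded at or closest to the blood draw, reported as a correlation or regression slope with 95% CI. This matches the title. Native thiol on systolic pressure is one example; the team may name another single pair.
3. State that controls do not enter this analysis.
4. Make other markers, other measures, and any severe/non-severe or early/late-onset contrast secondary, each with its cut defined.
5. Fix these choices before thiol results are seen. The document mixes future and past tense, so it is unclear whether the assays are still to come. If results already exist, label the severity analysis post hoc.

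**Cost:** a paragraph of plan text and possibly one data-collection line for the time of the chosen measurement relative to the draw. No extra women or assays are needed.

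**Downsides:** the team commits to one marker and one measure. A slope or correlation may miss a threshold relation. With 50 cases, correlations below about 0.39 are detected with less than 80% power, so the interval should carry the interpretation: an observed r of 0.40 would have a 95% CI of 0.14 to 0.61.

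### Does a primary endpoint that joins two questions over linked thiol markers, with no deciding marker, severity measure or alpha rule, call for a change to the plan?

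*Combined protocol and SAP*

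**What the plan says.** Section 4 gives one primary endpoint: "The primary endpoint in this analysis is to evaluate thiol/disulfide levels in preeclampsia and address its relationship with its severity". The official title describes the severity part as a correlation: "Serum Thiol/Disulphide Homeostasis level and its correlation with the severity of preeclampsia".

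Section 3 sets out the markers. Two are assayed: "The contents of the native thiol (-SH) and total thiol (-SH + -S-S-) in the serum samples will measure". The third is calculated: "Half of the difference between the total and native thiols will yield the dynamic disulfide (-S-S) content". The list of variables for the group comparison ends with "liver function tests (AST, ALT), thiol, disulphide, and infant weight at delivery", which does not say which thiol is meant.

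Section 2 names one test, Student's t-test, which "will be used for comparison of the thiol/disulfide levels by the variable groups formed". Section 1 says "There are two groups in the study": 50 women with preeclampsia and 50 healthy controls. Section 3 mentions early and late onset, for instance "All patients with early onset preeclampsia will hospitalize", and a blood pressure threshold of 160/110 mm Hg, but only when describing care.

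The document states no significance level, multiplicity rule, order of the two questions or sample-size calculation. It does not say whether the work is confirmatory or exploratory.

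**The concern.** A primary endpoint is meant to fix the main answer in advance. Here two questions share the label, two or three markers could answer each, and the severity question has neither a scale nor a test tied to it. If several unadjusted tests were run and the most favourable reported, a reader could not tell a planned result from a chosen one.

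The markers are also tied by arithmetic. Disulphide is half of total minus native thiol, so total = native + 2 x disulphide. Three significant markers would then not be three independent confirmations.

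At stake are the false-positive rate of the primary claim and, for severity, the meaning of the claim itself.

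**Working it through.** The plan gives no alpha, power or error rate, so there is no figure of its own to reproduce. What follows sizes the concern under stated assumptions.

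**Inputs from the document:** 50 cases and 50 controls (section 1); native thiol N and total thiol T measured, disulphide D = (T - N)/2 (section 3).

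**Inputs assumed:** two-sided 0.05 per test; no true difference anywhere; any significant marker counts; one severity test per marker within the 50 cases; correlation ρ of N with D from -0.5 to 0.9; ratio r = SD(D)/SD(N) from 0.05 to 0.87.

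**Step 1, the link.** Since T = N + 2D, its standardised test statistic is z_T = (z_N + 2r z_D)/s, with s² = 1 + 4r² + 4rρ. Three markers therefore carry only two dimensions. The figure for six independent tests, 1 - 0.95^6 = 26.5%, cannot apply.

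**Step 2, one question.** The chance that at least one |z| exceeds 1.96 is:

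| Markers tested | Per question | Both questions |
|---|---|---|
| One | 5% | 9.75% |
| Total thiol and disulphide | 5.8-9.7% | 11.2-18.5% |
| Native thiol and disulphide | 7.0-9.7% | 13.5-18.5% |
| All three | 7.0-12.2% | 13.6-22.9% |

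The highest value arises at ρ = -0.5, r = 0.5. There s² = 1 + 1 - 1 = 1, corr(N,T) = (1 + 2rρ)/s = 0.5 and corr(D,T) = (ρ + 2r)/s = 0.5, so the three markers are spread as far apart as the link allows. The lowest two-marker value arises at ρ = 0.9, r = 0.87. There s² = 1 + 3.028 + 3.132 = 7.160 and corr(D,T) = 2.64/2.676 = 0.987, so the two tests are nearly one.

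**Step 3, both questions.** A contrast within cases is uncorrelated with the mean of all cases, so the two questions are close to independent and the joint chance is 1 - (1 - p)². One marker: 1 - 0.95² = 9.75%. Three markers at the ceiling: 1 - 0.878² = 22.9%.

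**Step 4, check with t-tests.** Simulated t-tests (50 v 50, and cases split 25/25 by assumption) over a wider grid gave at most 22.9% for three markers. At ρ = 0 and r = 0.5, a 10/40 split gave 21.6% against 21.9% for 25/25. Raising ρ to 0.99 brought three markers down to about 11%.

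**Step 5, separating the sources.** Asking two questions accounts for 9.75% by itself. Leaving the marker open adds 5.8 - 5 = 0.8 to 12.2 - 5 = 7.2 percentage points per question.

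**Step 6, the price of error control.** Splitting alpha to 0.025 per question raises the difference detectable at 80% power from 0.566 to 0.625 SD for 50 v 50. Within cases it rises from 0.809 to 0.896 SD for a 25/25 split, and from 1.011 to 1.120 SD for 10/40 (both splits assumed). A fixed order avoids this loss but makes the second claim depend on the first.

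**The case for a change.** The strongest case for a change is that the plan uses the word primary and never calls itself exploratory. The missing items are not formalities: the deciding marker, the severity measure and its test could all be settled after the data are seen. Comparing cases with controls cannot answer a question about severity. A remedy would cost only some wording and one definition, with no new samples or assays. The false-positive range could also exceed 23% if several severity groupings or a thiol-to-disulphide ratio were added.

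The facts in this stand: none of those items is written down. The inference is weaker.

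- The group question is largely fixed. Section 3 lists thiol and disulphide for comparison in advance, and only the choice of thiol is open.
- The t-test in section 2 is worded broadly enough to cover severity groups once they are formed, so the gap is that no test is assigned to severity, not that none is available.
- Section 3 already collects blood pressure, urine protein, platelets, creatinine and liver enzymes, from which a severity measure or a correlation could be built.
- The rule that any significant marker counts is not in the document, whose endpoint speaks of evaluating and addressing and sets no threshold for success.
- Judging each question separately at 0.05 would be an acceptable choice, and it leaves the 9.75% exactly where it is.

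**Conclusion.** The observation is accurate, but no change to the plan follows. The plan omits detail; it does not prescribe a wrong analysis. Analysts can fill the gap in the ordinary way: show every marker for both questions with its estimate, say how severity was measured, and note that the markers are linked. The documents do not single out one marker or severity measure, so any choice would be the sponsor's.

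Formal error control is a fair trade-off here. It would cost detectable difference or tie one question to the other, in an observational study of 100 women that claims no error rate.

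The size is about 6-12% per question with two or three markers against 5% with one, and about 11-23% over both questions against 9.75%. These figures rest on an assumed two-sided 0.05, no true effects, any significant marker counting, one severity test per marker, a correlation of -0.5 to 0.9 and an SD ratio of 0.05 to 0.87. None of these is in the document. What remains is a caution for readers: interpret the severity result in the light of how severity was defined, and do not take agreement among the three markers as independent confirmation.
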